3.1. Variables

The following table lists all variables relevant to the analysis along with their ICD, OPS or ATC codes. For each patient, possible comorbidities will be recorded at baseline by including all outpatient and inpatient information coded within two years prior to the index hospitalization and during first hospitalization (exceptions are marked accordingly).

The "minor outpatient complications" defined below (see the last row of the following table) will be based exclusively on outpatient information coded after discharge of the first hospitalization.

All other variables concerning complications during follow-up will be collected exclusively from inpatient information during hospitalization and after discharge.

Variable	Classification	Code
Olecranon fracture	ICD	S52.01
Simple fracture TBW	OPS	5-793.27
Multi-fragmented TBW	OPS	5-794.17
Simple fracture LPF	OPS	5-793.k7
Multi-fragmented LPF	OPS	5-794.k7
Comorbidities at Baseline		
Alcohol abuses	ICD	E24.4, F10, G31.2, G62.1, G72.1, I42.6, K29.2, K70, K85.2, K86.0, T51.0, T51.9
Arthrosis	ICD	M15-M19 (only before index admission)
Atherosclerosis	ICD	I70
Atrial fibrillation and flutter	ICD	I48
Asthma		J45
Bone tumor/metastasis	ICD	C40.0, C79.5, C79.86, C79.9
Cancer	ICD	C
Chronic kidney disease	ICD	N18, N19
Chronic polyarthritis	ICD	M05, M06
Congestive heart failure	ICD	I50
Coronary heart disease	ICD	I25
Dementia	ICD	F00, F01, F02, F05.1, G30, G31.1
Depressive episode	ICD	F32, F33
Diabetes mellitus	ICD	E10-E14
Dorsalgia	ICD	M54
Hypertension	ICD	I10-I15
Infection	ICD	M86.02, M86.12, M86.22, M86.32, M86.42, M86.52, M86.62, M86.82, M86.92, T84.5, T84.6, T84.7 (only before index admission)
Neurotic, stress-related and somatoform disorders	ICD	F41, F43, F45
Nicotine abuses	ICD	F17
Obesity	ICD	E66
Osteoporosis	ICD	M80-M85
Parkinson	ICD	G20
Polytrauma	ICD, OPS, DRG	ICD: T07 , OPS: 5-982 , or coded DRG started with "W" (only during index hospitalization)
Elbow arthrosis	ICD	M25.52 (only before index admission)
Previous stroke	ICD	I60-I69 (only before index admission)
Prior level of care (LoC)		Level of care in the database (from 2017)
Problems related to care-provider dependency	ICD	Z74

Pharmaceutical therapy		
Any anticoagulant	ATC	B01AA, B01AB, B01AC, B01AE, B01AF, B01AX
Vitamin D or calcium	ATC	A11CC
Bisphosphonates	ATC	M05BA, M05BB
Any osteoporosis pharmacotherapy	ATC	Vitamin D/Calcium or Bisphosphonates
Contraceptives for topical use	ATC	G02B (only for matching)

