Minor outpatient complications (LPF and TBW) ¹	ICD	G56.1, G56.2, G56.3, I80.80, I80.81, M00.02 , M00.12, M00.22, M00.82, M00.92, M13.12, M13.82, M13.92, M19.12, M19.22, M19.82, M19.92, M24.02, M24.12, M24.22, M24.32, M24.42, M24.52, M24.62, M24.82, M24.92, M25.12, M25.22, M25.32, M25.42, M25.52, M25.62, M25.72, M25.82, M25.92, M61.02, M61.12, M61.22, M61.42, M61.52, M61.92, M62.02, M62.12, M62.22, M62.32, M62.42, M62.52, M62.62, M62.82, M62.92, M65.02, M65.12, M65.22, M65.82, M65.92, M84.02, M84.22, M84.32, M84.82, M84.92, M86.12, M86.22, M86.32, M86.42, M86.62, M86.82, M86.92, M87.22, M87.32, M87.82, M87.92, M89.52, M96.6, T79.60 , T81.4, T84.01, T84.11, T84.5, T84.6, T84.7
	OPS	All outpatient codes OPS for LPF or TBW coded collected above

Table 2: Definition of all variables

¹ Data collection exclusively based on outpatient information coded after discharge.

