4.1. Descriptive Statistics of Baseline Variables and Treatment trends

For descriptive analysis of treatment trends over time and baseline characteristics, the entire cohort will be used. For nominal and ordinal variables, the absolute and relative numbers will be calculated. All baseline parameter (see table 2 in chapter 3.1) will be reported for the entire cohort and grouped by treatment groups.

Time trends in the treatment of olecranon fractures using TBW vs LPF over study time will be presented as absolute and relative frequencies per year and possible trend will be tested via two-sided Cochran-Armitage trend test. Subgroup analyses, i.e. female/male patients or grouped by age, will be performed, if the data will be sufficiently large. All calculated p-values for time trends will be only calculated to illustrate the results and are in no way of a confirmatory nature. Therefore, the p-values in this part should be interpreted with caution.

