4.2. Analysis of Primary and Secondary Endpoints

To analyze differences in the treatment groups (TBW versus LPF), a 1:1 propensity score (PS) matching will be performed to guarantee sufficient balance between them. Each patient treated with TBW will be matched with a patients treated with LPF, based on age, sex, fracture complexity, year of treatment, all clinical relevant comorbidities and pharmaceutical therapy at index hospitalization (listed in table 2 “Comorbidities at Baseline” and “Pharmaceutical therapy”). Analysis set will defined by all patients included in the matching.

The balance will be evaluated using risk differences, z-differences and sum of squared z-differences (SSQZ) and will be reported for all variables before and after matching. The hyper-parameter (i.e. caliper with, distance for continuous variables, factors with exact matching) of the PS matching will be chosen in such way that the sum of squared z-differences (SSQZ) will be minimized around the number of variables included in the matching procedure (k), i.e.

$$k/2 \leq SSQZ \approx k.$$

Overlap between matching groups will be presented by the histogram of $logit(p_s)$. The dependency of the Matching partners and thus a stratified evaluation will not be considered.

In-hospital complications and 30-days mortality

All in-hospital endpoints as well as 30-day mortality are given by binary variables. Absolute and relative frequencies for both treatment group will be reported and differences between them will be tested via two-sided χ^2 -independence test. Moreover, a multivariable logistic regression model will be performed to adjust for patient's risk profile. Odds ratio (OR) comparing TBW and LPF for all in-hospital complications and 30-day mortality will be illustrated using forest plots.

30-day mortality will be defined as primary endpoint instead of in-hospital death to avoid bias due to differences in the LOS of both treatment groups. Absolute and relative frequencies for in-hospital death will be reported for the sake of completeness; however, p-values for possible differences will not be interpreted in a confirmatory manner.

Complications during follow-up

The start of observation will be defined by the day of surgery. Median follow-up time will be determined for the entire analysis set using Kaplan Meier estimate (death as censored event).

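### The baseline covariate 'Osteoporosis' is coded as all of M80-M85 and so takes in M84, which the same table uses for complications after elbow fixation

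*Combined protocol and SAP*

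**What the plan says.** All the definitions are in Table 2, section 3.1.

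- The baseline row reads "Osteoporosis ICD M80-M85". It names a whole range and carries no remark on timing.
- Baseline comorbidities come from inpatient and outpatient records "coded within two years prior to the index hospitalization and during first hospitalization (exceptions are marked accordingly").
- The last row of the table, minor outpatient complications, includes "M84.02, M84.22, M84.32, M84.82, M84.92". That endpoint "will be based exclusively on outpatient information coded after discharge of the first hospitalization".
- A neighbouring baseline row does carry a timing limit: "Elbow arthrosis ICD M25.52 (only before index admission"). The Arthrosis and Infection rows have the same limit.

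The covariate is then used in several places. Section 4.2 matches on the variables "listed in table 2 “Comorbidities at Baseline” and “Pharmaceutical therapy"). Section 4.1 states that every baseline parameter "will be reported for the entire cohort and grouped by treatment groups". Section 4.2 also plans multivariable Cox models of how baseline variables affect the endpoints. Under section 5, a variable is zero when no related code is found, so any listed code sets it.

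**The concern.** The plan treats M84 as evidence of osteoporosis in one row and as a local problem at the operated elbow in another. The second use sits among joint, bone-infection and bone-necrosis codes and is restricted to particular sub-codes. The first takes M84 at any site. Nothing in the plan explains why M84 should indicate osteoporosis.

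Bone quality is a plausible influence on both the choice of implant and the failure of fixation, and one of the study's two aims is to find independent predictors of a poor course. If the flag mixes patients with osteoporosis and patients who have only an M84 code, its hazard ratio does not describe what its name says. Good balance on the flag would also not establish balance on osteoporosis. The weighted analyses in section 4.3 would not reveal this, since their propensity score presumably uses the same flag.

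**Working it through.** The plan states no figure on this point, so there is none to reproduce. The check compares code lists and then adds an illustration of scale.

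**1. Overlap.** The minor outpatient complication row lists 80 ICD codes. Those falling in M80-M85 are M84.02, M84.22, M84.32, M84.82 and M84.92: five codes, all M84. None of M80, M81, M82, M83 or M85 appears there.

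**2. Comparison with the other baseline rows that share codes with that list.**

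| Baseline row | Shared codes | Counted only before index admission? |
|---|---|---|
| Arthrosis (M15-M19) | M19.12, M19.22, M19.82, M19.92 | Yes |
| Infection | M86.12, M86.22, M86.32, M86.42, M86.62, M86.82, M86.92, T84.5, T84.6, T84.7 | Yes |
| Elbow arthrosis | M25.52 | Yes |
| Osteoporosis (M80-M85) | M84.02, M84.22, M84.32, M84.82, M84.92 | No |

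In the first three rows the baseline label names the same kind of condition as the complication code. In the fourth it does not, and the timing limit is missing too.

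**3. Literal application.** Patient A has one outpatient M84.22 code 14 months before the fracture and nothing else in the range. Patient B has M81. Both are set to osteoporosis = 1, and neither the matching nor the models can tell them apart. Patient C has an M84 code only in the index stay. The flag is set here as well, and section 3.3 says that ICD codes within a case have no chronological order, so the code cannot be placed before or after surgery.

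**4. Scale, on assumed inputs only.** Let p be the share of patients who have osteoporosis and carry a code for it. Let q be the share of the remaining patients whose only code in the range is M84. The documents give neither. The share of flagged patients without osteoporosis is

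f = (1 − p)q / [p + (1 − p)q].

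Example: p = 5%, q = 1% gives 0.95 × 0.01 / (0.05 + 0.0095) = 0.0095 / 0.0595 = 16.0%.

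| p (assumed) | q = 0.1% | q = 0.5% | q = 1% | q = 3% |
|---|---|---|---|---|
| 5% | 1.9% | 8.7% | 16.0% | 36.3% |
| 15% | 0.6% | 2.8% | 5.4% | 14.5% |
| 30% | 0.2% | 1.2% | 2.3% | 6.5% |

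The answer runs from negligible to about a third, depending wholly on q. Dilution is greatest where osteoporosis is rarest. If prevalence rises with age, that is the separate study of patients under 70.

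**5. After the change.** With M84 removed, the overlap in step 1 falls from five codes to none.

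**The case against.** Several objections have force.

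- **Dual use is part of the design.** A reader might infer that a code cannot properly be both covariate and complication, or that events are counted twice. The documents do not support that. The windows are separate, and Arthrosis, Infection and Elbow arthrosis share codes in the same way. What remains is a label that does not fit M84.
- **The plan does not print what M84 means.** That the five codes are local elbow problems is inferred from where they are listed and from the plan's label for M25.52, which suggests that the final digit 2 marks the elbow. Extending this to M84 at other sites assumes that the site digit changes the location and not the kind of condition. This limit stands. It is also why M83 and M85 are left for the sponsor to check and are not called wrong here.
- **Such codes may be rare at baseline.** Previous treatment of an olecranon fracture is an exclusion, which should reduce elbow-site M84 codes before the index stay. This is a fair point, although the row accepts M84 at any site.
- **The index injury.** It is tempting to suppose that M84 would be entered for the fracture itself. Nothing in the documents suggests so, as the injury is identified by S52.01. The row merely allows an index-stay M84 code to count.
- **The treatment comparison.** A reader might infer residual confounding of TBW versus LPF. That would require the mix of true and false flags to differ between the arms after matching, which nothing here shows. Age, sex, bisphosphonates and vitamin D or calcium are also matched on and carry part of the same information.
- **A broad bone-disorder covariate may be intended.** If so, renaming the row would correct the label. It would still merge M84 with osteoporosis in one risk-factor estimate.

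**Conclusion.** The point holds as a minor coding error. Read literally, the 'Osteoporosis' row flags patients whose only code in the range is M84, a category that the plan itself uses for complications after fixation. Alone among the four rows in the comparison, it also accepts codes from the index stay.

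How many patients this concerns, or whether there are any, cannot be determined from the documents. The table of assumed values shows how much the answer depends on the unknown frequency and should not be read as an estimate. The main consequence is for the osteoporosis hazard ratio and the baseline and balance tables. The direction of error in the hazard ratio is not fixed. It moves towards no effect if M84-only patients carry no excess risk, and could move the other way if they carry a high risk of their own. The effect on the TBW-LPF contrast is probably small.

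The conclusion rests on two assumptions: that M84 in the baseline row means the same kind of condition as M84 in the complication row, and that the osteoporosis flag is among the baseline variables in the regression models. Section 4.2 implies the second without listing the model terms.

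**What to change.** Remove M84 from the 'Osteoporosis' row of Table 2, and have the sponsor check each remaining code of the range against the label, keeping those that denote osteoporosis. If the conditions coded as M84 are wanted as a covariate, give them their own row, counted only before the index admission as for Arthrosis and Infection. Make the change before the propensity score is fitted, so that matching, balance tables, weights and regression models all use the same definition.

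The cost is a one-line change to the code list and a slightly lower reported prevalence of osteoporosis. A separate M84 row would add one variable to the matching set, and so one to k in the balance target of section 4.2.

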Hormonal contraceptives for systemic use	ATC	G03A (only for matching)
General Complications		
Acute liver failure	ICD	K72.0, K72.7, K72.9
Acute myocardial infarction	ICD	I21, I22
Acute renal failure	ICD	N17
Acute respiratory distress syndrome	ICD	J80
Cardiac arrest	ICD	I46
Deep vein thrombosis	ICD	I80.1, I80.2, I82.2, I82.3
Delirium	ICD	F05
Pulmonary embolism	ICD	I26
Sepsis	ICD	A41, A40, B37.7, R65.0, R65.1, R65.9, R57.2
Stroke	ICD	I60-I64
Ischemic stroke	ICD	I63-I64
Resuscitation	OPS	8-77 (also defined as complication, if it happens on the same day as surgery)
Intensive care	OPS	8-980, 8-98f (only during hospital stay)
Blood transfusion	OPS	8-800.0, 8-800.1, 8-800.c (only during hospital stay)
Surgical complications (at least one day after surgery)		
Conversion to TBW	OPS	5-793.27, 5-794.17
Conversion to LPF	OPS	5-794.k7, 5-793.k7
Endoprosthetic joint and bone replacement	OPS	5-824.40, 5-824.41, 5-824.50, 5-824.51, 5-824.52
Conversion to other fracture fixation	OPS	5-790.07, 5-790.17, 5-790.27, 5-790.37, 5-790.47, 5-790.57, 5-790.67, 5-790.97, 5-790.d7, 5-790.k7, 5-790.m7, 5-790.n7, 5-790.p7, 5-790.x7, 5-793.17, 5-793.37, 5-793.67, 5-793.77, 5-793.87, 5-793.97, 5-793.a7, 5-793.b7, 5-793.c7, 5-793.g7, 5-793.h7, 5-793.m7, 5-793.n7, 5-793.x7, 5-794.07, 5-794.27, 5-794.57, 5-794.67, 5-794.77, 5-794.87, 5-794.a7, 5-794.b7, 5-794.c7, 5-794.g7, 5-794.m7, 5-794.n7, 5-794.x7
Conversion, any	OPS	Any conversion as defined above
Upper limb amputation, ipsilateral (exarticulation elbow or forearm)	OPS	5-862.2, 5-862.3, 5-862.4
Bursitis	ICD	M70.2, M70.3 (only during hospital stay)
Compartment syndrome	ICD	S51.86 (only during hospital stay)

Consequences of injury of the upper extremity	ICD	T92.1 (only during hospital stay)
Haematoma after surgery	ICD	T81.0 (only during hospital stay)
Implant dislocation	ICD	T84.11 (only during hospital stay)
Mechanical malfunction or material failure/loosening	ICD	T85.88, T85.9 (only during hospital stay)
Peri-prosthetic or peri-implant fracture	ICD	M96.6, T84.11 (only during hospital stay)
Surgical incidents	ICD	Y69, Y82.8, Y84.9 (only during hospital stay)
Delayed union (if coded within six months)	OPS	5-781.a7, 5-782.17, 5-782.27, 5-782.37, 5-782.47, 5-782.57, 5-782.a7, 5-782.b7, 5-782.x7, 5-784.07, 5-784.17, 5-784.27, 5-784.37, 5-784.47, 5-784.77, 5-784.87, 5-784.b7, 5-784.c7, 5-784.d7, 5-784.e7, 5-784.f7, 5-784.x7

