Implant removal (TBW)	OPS	5-787.07, 5-787.17, 5-787.27, 5-787.67, 5-787.77, 5-787.g7, 5-810.34, 5-810.35
Revision of the osteosynthesis (LPF and TBW)	OPS	5-785.07, 5-785.17, 5-785.27, 5-785.37, 5-785.47, 5-785.57, 5-785.67, 5-785.77, 5-789.37, 5-78a.07, 5-78a.17, 5-78a.27, 5-78a.57, 5-78a.67, 5-78a.77, 5-78a.87, 5-78a.97, 5-78a.c7, 5-78a.g7, 5-78a.k7, 5-78a.m7, 5-78a.n7, 5-78a.x7, 5-793.07, 5-793.17, 5-793.27, 5-793.37, 5-793.67, 5-793.77, 5-793.87, 5-793.97, 5-793.a7, 5-793.b7, 5-793.c7, 5-793.g7, 5-793.h7,

		5-793.k7, 5-793.m7, 5-793.n7, 5-793.x7, 5-794.07 , 5-794.17, 5-794.27, 5-794.57, 5-794.67, 5-794.77, 5-794.87, 5-794.a7, 5-794.b7, 5-794.c7, 5-794.g7, 5-794.h7, 5-794.k7, 5-794.m7, 5-794.n7, 5-794.x7, 5-824.4 , 5-824.5, 5-825.01 , 5-825.4, 5-825.a, 5-825.m
Resection arthroplasty (for spacer placement)	OPS	5-829.4
Secondary arthroplasty	OPS	5-824.4 , 5-824.5
Arthrolysis	OPS	5-800.64 , 5-800.65, 5-810.24 , 5-810.25, 5-810.94, 5-810.95
Classification of complications and long-term endpoints/events		
Major adverse event		resuscitation, cardiac arrest, myocardial infarction, stroke, acute renal failure, acute liver failure, acute respiratory distress syndrome, sepsis or death from any case
Thromboembolic event		Deep vein thrombosis, pulmonary embolism, ischemic stroke or death from any case
Surgical complications		Adhesive capsulitis, arthrolysis, debridement, frozen elbow, implant removal within first 3 months, infection, infection with antibiotic-resistant germs, joint damage/cartilage damage, luxation, delayed union, non-union/pseudoarthrosis, malunion, nerve injury, vascular injury, osteonecrosis, postoperative stiffness, secondary arthroplasty, secondary arthroscopy, secondary surgery (open) including revision surgery, upper limb amputation
Implant-associated complications (IAC)		Impingement, bursitis, mechanical malfunction or material failure/loosening, periprosthetic or periimplant fracture
Non-implant associated complications (non-IAC)		Infection, infection with antibiotic-resistant germs, hematoma after surgery

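### Prior DVT and PE are missing from the baseline variables although prior stroke is included, so no thromboembolic analysis accounts for them and the anticoagulant hazard ratio may be partly confounded

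*Combined protocol and SAP*

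**What the plan says.** Section 3.1, Table 2 defines a thromboembolic event as "Deep vein thrombosis, pulmonary embolism, ischemic stroke or death from any case". Table 4 (section 3.2.2) lists it as a secondary endpoint, both as time to event and as an in-hospital yes/no outcome.

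Among the baseline comorbidities, Table 2 has a previous-stroke row, "I60-I69 (only before index admission"). The DVT codes, "I80.1, I80.2, I82.2, I82.3", and the code I26 for "Pulmonary embolism" stand only under General Complications. No baseline row contains them.

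Baseline comorbidities are taken from inpatient and outpatient codes "within two years prior to the index hospitalization and during first hospitalization", unless a row says otherwise. The variable for any anticoagulant pools "B01AA, B01AB, B01AC, B01AE, B01AF, B01AX" and, unlike the contraceptive rows, is not reserved for matching.

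Section 4.2 builds the propensity score from age, sex, fracture complexity, treatment year and "all clinical relevant comorbidities and pharmaceutical therapy at index hospitalization", with a pointer to the two Table 2 lists. It also plans multivariable Cox models of baseline variables for TE, with hazard ratios shown in forest plots. Section 4.3 repeats the TE and in-hospital TE regressions in the whole cohort, unweighted and with three sets of propensity weights. The introduction names the identification of independent risk factors as part of the study aim.

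**The concern.** Of the three non-fatal TE components, one has its history recorded and two do not. The section 4.2 covariate list is closed by its reference to Table 2, so nothing elsewhere in the plan supplies the missing history. The section 4.3 analyses cannot expose the gap: the weights come from a propensity score without the variable, and the unweighted regression does not contain it either.

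What is at stake is mostly the risk-factor aim. The covariate hazard ratios are reported as results. Several conditions that may lead to anticoagulant use (atrial fibrillation, coronary heart disease, previous stroke) are baseline variables, but earlier venous thrombosis is not. If it raises the risk of TE and also leads to anticoagulant use, part of its effect will appear in the anticoagulant hazard ratio. A null or protective drug association could then look less favourable than it is. In addition, balance between TBW and LPF on prior DVT/PE is neither sought nor shown.

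**Working it through.** **Rows side by side (Table 2)**

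| TE component | Outcome codes | Pre-index history row |
|---|---|---|
| Ischemic stroke | I63-I64 | Yes, I60-I69 |
| DVT | I80.1, I80.2, I82.2, I82.3 | None |
| PE | I26 | None |

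Infection is handled like stroke: the M86 and T84 codes form a pre-index row and are also complications.

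The plan gives no prevalence of prior DVT/PE, no effect size and no TE event count, so there is no figure to reproduce. The calculations below are illustrations, and every numerical input is an assumption.

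**Anticoagulant hazard ratio, true value 1.0**

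Inputs: prevalence v of prior DVT/PE, its hazard ratio H for TE, anticoagulant use c among patients with that history and d among those without.

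- P(V|AC) = vc / [vc + (1−v)d]
- P(V|no AC) = v(1−c) / [v(1−c) + (1−v)(1−d)]
- Apparent HR ≈ [1 + P(V|AC)(H−1)] / [1 + P(V|no AC)(H−1)]

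| v | c / d | H | P(V given AC) | P(V given no AC) | Apparent HR |
|---|---|---|---|---|---|
| 3% | 60% / 30% | 1.5 | 0.018/0.309 = 0.058 | 0.012/0.691 = 0.017 | 1.029/1.009 = 1.02 |
| 5% | 60% / 20% | 2 | 0.030/0.220 = 0.136 | 0.020/0.780 = 0.026 | 1.136/1.026 = 1.11 |
| 5% | 60% / 20% | 3 | 0.136 | 0.026 | 1.273/1.051 = 1.21 |
| 5% | 60% / 20% | 4 | 0.136 | 0.026 | 1.409/1.077 = 1.31 |

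A wider grid (v 1-5%, overall anticoagulant use a of 10-35%, c 40-90%, H 1.5-3) runs from about 1.00 to 1.88. The top needs v = 5%, a = 10%, c = 90% and H = 3. Then P(V|AC) = 0.05 × 0.9/0.1 = 0.45, P(V|no AC) = 0.05 × 0.1/0.9 = 0.0056, and 1.90/1.011 = 1.88. That corner requires 45% of all users to have had DVT or PE.

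**How far anticoagulant use can stand in for prior DVT/PE**

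R² = [P(V|AC) − P(V|no AC)]² × a(1−a) / [v(1−v)]. Over the same grid it runs from about 0 to 0.37. The maximum is 0.444² × 0.09/0.0475 = 0.37. Most of the variation in history is therefore not carried by the drug variable.

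**TBW versus LPF**

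With prevalences p1 and p0 in the matched arms, the bias factor is [1 + p1(H−1)] / [1 + p0(H−1)].

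- Equal prevalence: 1.00 for any H.
- 4% vs 2%, H = 2: 1.04/1.02 = 1.02.
- 5% vs 1%, H = 3: 1.10/1.02 = 1.08.
- 5% vs 1%, H = 4: 1.15/1.03 = 1.12.

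**The case against.** The strongest reply is that little depends on this. TE and in-hospital TE are secondary, and the Bonferroni-Holm adjustment in section 4.2 covers primary endpoints only, so no confirmatory result changes. Nothing in the documents suggests that earlier thrombosis steers the choice between plate and wire. The plan also does not promise a history row for every outcome component: acute renal failure, acute liver failure, ARDS and sepsis have none under their own codes. All of this stands, and it limits the weight of the point. It does not explain why history is kept for one non-fatal TE component and not for the other two when covariate effects are to be reported.

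The calculation can also be attacked fairly. It uses two variables only, does not condition on the other indications, and fixes the true drug effect at 1.0. Conditioning could move the figure either way, and if the true ratio were below 1 the omission would mask protection rather than create apparent harm. Section 4.2 does not list the TE model's covariates, so the presence of anticoagulants in it is an inference, though a natural one.

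A reader might infer several stronger things:

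- **That a main predictor of TE is missing.** The composite includes all-cause death and ischemic stroke, and the documents do not give the share of events that are DVT or PE.
- **That the effect of prior DVT/PE is attributed to anticoagulant use.** The drug variable pools six ATC groups and sits beside several other indications, so it can take up only part of that effect.
- **That old diagnoses are counted as new events.** They may be, since section 3.3 says ICD codes have no order within a case. No frequency is given, follow-up TE events come from inpatient data only, and a history flag cannot separate a re-coded thrombosis from a recurrence.
- **That systemic contraceptives, "G03A (only for matching"), are wrongly kept out of the outcome model.** The plan already seeks balance on them through matching; going further is a modelling preference.

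**Conclusion.** The omission is verifiable from Table 2 and section 4.2: no planned matching, balance check, TE regression or weighting accounts for prior DVT/PE. It matters chiefly for interpreting the anticoagulant hazard ratio in the TE risk-factor model, which may be partly confounded by this indication. The illustrative size is 1.02-1.31 for a true ratio of 1.0, and it rests wholly on assumed prevalence, effect and drug-use figures; other assumptions widen the range.

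The documents do not support the reading that the treatment comparison is biased. That requires prior DVT/PE to differ between the matched arms. Even at 5% vs 1% the factor is 1.08 with a hazard ratio of 3 and 1.12 with 4, and at equal prevalence it is 1.00. This is a cheap improvement to a secondary, risk-factor analysis, not a threat to the primary endpoints.

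**What to change.** Add one row to the baseline comorbidities in Table 2: *Previous DVT/PE*, ICD I26, I80.1, I80.2, I82.2, I82.3, restricted to codes before the index admission, using the existing two-year look-back. The restriction is essential, because the same codes during the index stay are outcomes and carry no timing; without it the covariate would contain the event.

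Include the row in the propensity score, the balance table, the weights of section 4.3 and the TE and in-hospital TE models. State in section 4.2 that the anticoagulant hazard ratio is not to be interpreted causally.

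Optionally, run a TE sensitivity analysis that does not count DVT/PE codes as events in patients with prior DVT/PE. It must be labelled as also removing true recurrences, which lowers the estimated effect of that history. No change to the contraceptive rows is needed.

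The cost is one more covariate. The codes are already in the plan, and the exclusion criteria already require complete insurance status for the two years before index. History older than the look-back would still be missed unless it was coded again.

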Infection	ICD	T84.5, T84.6, T84.7, M86.02, M86.12, M86.22, M86.32, M86.42, M86.52, M86.62, M86.82, M86.92 (only during hospital stay)
	OPS	5-780.47, 5-780.57, 5-780.67, 5-780.77, 5-780.87, 5-780.97, 5-785.17, 5-785.57, 5-785.77, 5-800.24, 5-800.25, 5-800.34, 5-800.35, 5-800.a4, 5-800.a5, 5-800.b4, 5-800.b5, 5-810.14, 5-810.15, 5-810.74, 5-810.75, 5-810.84, 5-810.85, 5-850.h2, 5-850.j2, 5-892.37, 5-892.47, 5-896.27, 8-989, 8-989.0, 8-989.1, 8-989.2, 8-989.3, 8-989.4, 8-989.5, 8-989.6
Infection, resistant	ICD	U80-83 (only during hospital stay)
	OPS	8-987
Joint damage / cartilage damage	OPS	5-780.37, 5-784.57, 5-784.67, 5-800.84, 5-800.85, 5-810.44, 5-810.45, 5-812.04, 5-812.05, 5-812.34, 5-812.35, 5-812.94, 5-812.95, 5-812.a4, 5-812.a5, 5-812.e4, 5-812.e5, 5-812.f4, 5-812.f5, 5-812.g4, 5-812.g5, 5-812.h4, 5-812.h5, 5-812.k4, 5-812.k5, 5-812.m4, 5-812.m5
Luxation	OPS	8-201.4, 8-201.5 (also including outpatient sector after discharge)
Malunion	OPS	5-781.07, 5-781.17, 5-781.27, 5-781.37, 5-781.47, 5-781.57, 5-781.67, 5-781.77, 5-781.87, 5-781.97
Nerve injury	OPS	5-040.1, 5-040.2, 5-040.3, 5-041.1, 5-041.2, 5-041.3, 5-044.1, 5-044.2, 5-044.3, 5-045.1, 5-045.2, 5-045.3, 5-046.1, 5-046.2, 5-046.3, 5-047.1, 5-047.2, 5-047.3, 5-048.1, 5-048.2, 5-048.3, 5-049.1, 5-049.2, 5-049.3, 5-04b.1, 5-04b.2, 5-04b.3, 5-050.1, 5-050.2, 5-050.3, 5-051.1, 5-051.2, 5-051.3, 5-052.1, 5-052.2, 5-052.3, 5-053.1, 5-053.2, 5-053.3, 5-054.1, 5-054.2, 5-054.3, 5-055.1, 5-055.2, 5-055.3, 5-056.1, 5-056.2, 5-056.3, 5-057.1, 5-057.2, 5-057.3 (only during hospital stay)
Non-union / Pseudoarthrosis (if coded after six months)	OPS	5-781.a7, 5-782.17, 5-782.27, 5-782.37, 5-782.47, 5-782.57, 5-782.a7, 5-782.b7, 5-784.07, 5-784.17, 5-784.27, 5-784.37, 5-784.47, 5-784.77, 5-784.87, 5-784.b7
Osteonecrosis	ICD	M87.22, M87.32, M87.82, M87.92
Postoperative stiffness, Adhesive capsulitis, Frozen elbow	OPS	5-800.64, 5-800.65, 5-800.c4, 5-800.c5, 5-810.24, 5-810.25, 5-810.94, 5-810.95

Vascular injury	OPS	5-388.12, 5-395.12, 5-397.12 (only during hospital stay)

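### T81.4 and the five M00.x2 codes count only as outpatient diagnoses, so an inpatient infection recorded by them alone enters none of the primary endpoints IH-non-IAC, IH-SC and SC

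*Combined protocol and SAP*

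**What the plan says.** All code lists are in Table 2 of Section 3.1.

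- **In-hospital Infection, ICD part:** "T84.5, T84.6, T84.7, M86.02, M86.12, M86.22, M86.32, M86.42, M86.52, M86.62, M86.82, M86.92 (only during hospital stay". These are 12 codes.
- **In-hospital Infection, OPS part:** a list beginning "5-780.47, 5-780.57, 5-780.67, 5-780.77, 5-780.87, 5-780.97, 5-785.17". It has 36 codes and no restriction to the hospital stay.
- **MOC row:** includes "M00.02 , M00.12, M00.22, M00.82, M00.92" and, at its end, "T79.60 , T81.4, T84.01, T84.11, T84.5, T84.6, T84.7".
- **Data sources:** the text before Table 2 limits MOC to outpatient records after discharge. All other follow-up complications come from inpatient records, during the stay and afterwards.
- **Composites:** non-implant-associated complications (non-IAC) have three components: "Infection, infection with antibiotic-resistant germs, hematoma after surgery". Infection is also a component of surgical complications (SC).
- **Endpoints:** Table 3 makes SC, IH-SC and IH-non-IAC primary. MOC is secondary (Table 4).
- **Bursitis and loosening:** "M70.2, M70.3 (only during hospital stay" and "T85.88, T85.9 (only during hospital stay". Both enter only the implant-associated composite (IAC), whose single endpoint covers the index hospitalization.

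**The concern.** By putting the six codes in the MOC list, the plan has already judged them to be complications of this surgery. It then reads them only in the setting where they are labelled minor. A patient whose wound or joint infection is diagnosed in hospital and treated without a listed operation has no event in the primary endpoints meant to capture it.

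Three primary endpoints are affected, and Section 4.2 puts the treatment comparisons of all primary endpoints into one Bonferroni-Holm family. IH-non-IAC is the most exposed. It has only three components, and it lacks the broad lists of repeat surgery and arthroscopy that SC and IH-SC contain.

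**Working it through.** The plan states no figure on this point. The check compares code lists and traces each code to its endpoints.

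**Step 1: where each code is read.**

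| Codes | In-hospital complication row | Baseline Infection row | MOC ICD list |
|---|---|---|---|
| T84.5, T84.6, T84.7 and seven M86 codes (.12, .22, .32, .42, .62, .82, .92) | yes (Infection) | yes | yes |
| M86.02, M86.52 | yes (Infection) | yes | no |
| T81.4, M00.02, M00.12, M00.22, M00.82, M00.92 | **no** | **no** | yes |
| M96.6, T84.11 | yes (implant rows) | not applicable | yes |
| M70.2, M70.3, T85.88, T85.9 | yes (implant rows) | not applicable | **no** |

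Of the 12 Infection ICD codes, 10 are also in MOC, so reading an infection code in both settings is the plan's usual practice. For the six codes at issue, 6 of 6 are in MOC and 0 of 6 are in any inpatient complication row.

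**Step 2: whether Section 3.3 explains the gap.** That section says ICD codes carry no side, and therefore rests SC during follow-up mostly on procedures. In hospital, however, the plan accepts T81.0 (haematoma), T84.5-T84.7 and the M86 codes without a side. Timing does not explain it either: Section 3.3 counts every listed ICD code in the index case as an in-hospital complication, because no order within a case is available.

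**Step 3: what still captures such a patient.**

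- *IH-non-IAC, IH-SC and SC:* one of the 36 Infection OPS codes; a resistance code (ICD U80-83 or OPS 8-987); or a T84.5-T84.7 or M86 code recorded beside T81.4 or M00.x2.
- *IH-SC and SC only:* also the open secondary surgery and secondary arthroscopy lists.
- *IH-MAE (secondary):* a sepsis code.

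The events lost from the three primary endpoints are those with one of the six diagnoses and none of the applicable codes above.

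**Step 4: direction and size.** Let r1 and r2 be the true infection risks in the two arms, and q the share recorded only by these six codes. If q is the same in both arms, the observed risks are (1 - q)r1 and (1 - q)r2.

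- Risk ratio: (1 - q)r1 / [(1 - q)r2] = r1 / r2, unchanged. The odds ratio is nearly unchanged while events are rare.
- Risk difference: (1 - q)(r1 - r2), reduced by the factor (1 - q).
- Expected infection events: reduced by the factor (1 - q), so precision falls.

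If the shares differ, the risk ratio is multiplied by (1 - q1)/(1 - q2). The documents give none of r1, r2, q1 or q2. In the composites the effect is diluted by the other components.

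**The case against.** The strongest reply is that the net is already wide. Infections that lead to a listed operation are found in the index stay and at readmission. Resistance codes, sepsis codes and co-recorded T84 or M86 codes catch others. This stands, and it limits the point to infections recorded by diagnosis alone.

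A second reply is that the plan is consistent: the baseline Infection row holds the same 12 ICD codes as the outcome row, so adding codes to the outcome alone would create a mismatch in a matching covariate. This also stands, and the fix must cover both rows.

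Third, the documents do not describe T81.4 or M00.x2 in words, and the MOC list runs in code order, so position proves little. Reading them as post-procedural infection and pyogenic arthritis relies on the ordinary meaning of the classification.

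A reader might go further and infer that bursitis and loosening are missed where they matter most. The documents do not support that. Loosening or irritation that leads to surgery reaches Revision or Implant removal, both primary, and outpatient procedures can count in MOC. IAC has only an index-stay endpoint, so the stay restriction fits its use. No rule requires MOC to mirror the inpatient rows: T81.0, S51.86, T92.1 and the Y codes are absent from it too. What remains is a narrow inconsistency with M96.6 and T84.11. Bursitis or loosening recorded after discharge by diagnosis alone counts in no endpoint.

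**Conclusion.** The point holds for infection, in limited form. Followed as written, an inpatient T81.4 or M00.x2 diagnosis with none of the applicable capturing codes enters none of IH-non-IAC, IH-SC and SC, and the plan gives no reason for the omission.

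The size cannot be computed from the documents. Any percentage would only repeat an assumed infection risk and an assumed coding share. A reader might also infer a bias towards one implant. Nothing in the documents shows that these codes are used differently after TBW and LPF; under equal use, the effect is fewer events and less precision.

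The conclusion rests on the usual meaning of the six codes. It does not depend on how the undefined term hospital stay is read, since the codes are absent from every inpatient complication row. That term does decide whether added codes would also count at readmission. The bursitis and loosening gap is secondary and affects no primary endpoint.

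**What to change.** 1. Add T81.4, M00.02, M00.12, M00.22, M00.82 and M00.92 to the hospital-stay ICD list of the Infection row, or state why they are left out.
2. Add the same six codes to the baseline Infection row (before index admission), so that covariate and outcome stay aligned. This remains one matching variable, so the count k in the balance criterion of Section 4.2 does not change.
3. State whether the hospital-stay restriction on the Infection ICD codes means the index case series or any inpatient stay.
4. Optional: add M70.2, M70.3, T85.88 and T85.9 to the MOC list beside M96.6 and T84.11, or state that diagnosis-only bursitis and loosening after discharge are not captured. This changes MOC only.

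The cost is an edit to Table 2, a rerun of the query on data already held, and a rerun of the matching because a baseline covariate changes. There is a small downside: the codes carry no side, T81.4 has no site, and an infection present before surgery could be counted because ICD codes have no order within a case. The plan already accepts these limits for T81.0 and T84.5-T84.7.
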